1. INTRODUCTION AND BACKGROUND

1.1 Background

E-cigarettes have become a popular alternative to cigarette smoking globally and are garnering significant attention as potentially reduced exposure products and smoking cessation products. E-cigarettes consist of a battery, heating component, and a reservoir (often referred to as a pod, cartridge, or tank) containing tobacco-derived nicotine in a solution composed of glycerin and/or propylene glycol and flavorings. Upon activation, the heating element heats the solution and the consumer inhales the resulting vapor.

Because e-cigarette use does not involve the combustion of tobacco, it is expected that e-cigarette consumers will experience reduced exposure to most biomarkers of tobacco exposure compared to combustible cigarettes. Previous studies have shown that switching from combustible cigarettes to e-cigarettes with high rates of compliance results in large reductions in a number of cigarette smoke toxicants (Cravo et al. 2016, Goniewicz et al. 2017, O'Connell et al. 2016, McRobbie et al. 2015, Hecht et al. 2015). This study will evaluate a number of urine and blood biomarkers commonly associated with tobacco exposure during a 56-day period of use of the *my*bluTM e-cigarette system. Subjects randomized to the *my*bluTM study arm will be allowed to choose from one of four e-liquids (Tobacco Chill or Honeymoon flavor Intense e-liquids, containing either 2.5% or 4.0% nicotine) rather than be randomized to a particular flavor that they may not prefer to better represent the flavor selection that e-cigarette consumers experience while choosing a product in real-life situations. In addition, several BoPH, physiological assessments related to cigarette smoking health outcomes, subjective effects, and nicotine uptake will also be assessed.

1.2 *my*bluTM **Previous Clinical Experience**

One previous clinical study has been conducted with the mybluTM closed system (FON-01blu-2018). Fifteen healthy adult smokers enrolled in an open-label, 6-period crossover study to characterize nicotine uptake and subjective effects during a 10-puff controlled exposure (puffs 3 seconds in duration, taken at approximately 30-second intervals) relative to usual brand combustible cigarettes and the blu PRO open system product and to determine the potential impact of a nicotine salt e-liquid (with lactic acid).

Blood samples for plasma nicotine analysis were collected approximately 5 minutes prior to and at 2, 3, 4, 5, 6, 7, 8, 9, 10, 12, 15, and 30 minutes following the start of product use. The subjective effects questionnaires were completed at approximately 20 minutes following the start of each product use and included 6 questions presented on a scale of 1 (not at all) to 7 (extremely).

Nicotine AUC₀₋₃₀ and C_{max} increased with increasing nicotine content in the *my*bluTM products (16 – 40 mg nicotine), and was higher in the 25 mg nicotine salt formulation compared to the non-salt formulation. The time to reach maximal plasma nicotine concentrations (T_{max}) ranged from approximately 6.0 - 7.9 minutes following use of *my*bluTM and blu PRO products with nicotine salts and approximately 8.0 minutes following use of *my*bluTM non-salt formulation. AUC₀₋₃₀ and C_{max} to nicotine were lowest following use of blu

PRO compared to all other products tested. Overall exposure over 30 minutes (AUC₀₋₃₀) and peak exposure (C_{max}) to nicotine was highest following use of cigarette compared to any other product tested. The time to reach peak exposure (T_{max}) was shorter following use of the five e-cigarette test products compared to the cigarette.

Arithmetic Mean Baseline Adjusted Plasma Nicotine Concentration-Time Profiles Following Fixed Product Use by Product (Linear Scale)

Summary of Baseline Adjusted Plasma Nicotine Pharmacokinetics by Study Product

	Product A:	Product B:				
	my blu™	my blu™ 25 mg	Product C:	Product D:	Product E:	Product F:
Parameter	25 mg	(free-base)	my blu ^{тм} 40 mg	my blu ^{тм} 16 mg	blu PRO 48 mg	Cigarette
AUC ₀₋₃₀	125.2 (53.4)	98.99 (35.8)	190.7 (71.8)	118.5 (60.8)	84.84 (89.8)	324.9 (35.8)
(ng*min/mL)	[n=13]	[n=14]	[n=15]	[n=15]	[n=14]	[n=15]
C _{max} (ng/mL)	7.576 (80.6)	5.048 (49.9)	10.27 (83.6)	6.510 (76.5)	4.845 (108.3)	17.81 (49.6)
	[n=13]	[n=14]	[n=15]	[n=15]	[n=14]	[n=15]
T_{max} (min)	6.033	8.034	7.900	6.967	6.908	8.050
	(4.58, 16.77)	(2.28, 15.10)	(1.97, 15.00)	(3.98, 15.05)	(2.35, 15.03)	(5.00, 15.13)
	[n=13]	[n=14]	[n=15]	[n=15]	[n=14]	[n=15]

AUC and C_{max} are presented as geometric mean and geometric coefficient of variability %, T_{max} values are presented as median (min, max).

n: number of observations included in the summary statistics

Product A: *my*blu[™] closed system with CF Cosmic Fog Chilled Tobacco flavor, nicotine salt liquid 25 mg Product B: *my*blu[™] closed system with CF Cosmic Fog Chilled Tobacco flavor, non-nicotine salt liquid 25 mg Product C: *my*blu[™] closed system with CF Cosmic Fog Chilled Tobacco flavor, nicotine salt liquid 40 mg Product D: *my*blu[™] closed system with CF Cosmic Fog Chilled Tobacco flavor, nicotine salt liquid 16 mg Product E: blu PRO open system with Purilum Cosmic Fog Chilled Tobacco flavor, nicotine salt liquid 48 mg Product F: Subject's usual brand combustible cigarette

Mean scores for the subjective effects assessments tended to be highest after combustible cigarette use and generally followed by *my*bluTM 40 mg. With the exception of the questions "was it enough nicotine?" and "was it too much nicotine?", the responses following use of the 25 mg salt formulation were comparable to the 25 mg non-salt formulation.

	Study Products					
	Α	В	С	D	Е	F
Questions	n =13	n=14	n =15	n =15	n=14	n =15
Did it make you dizzy?	2.1 ± 1.32	1.9 ± 1.73	2.8 ± 1.78	1.5 ± 0.74	1.7 ± 0.99	3.7 ± 1.80
Did it make you nauseous?	1.2 ± 0.44	1.3 ± 0.83	1.4 ± 0.91	1.1 ± 0.26	1.4 ± 0.84	1.9 ± 1.44
Did you enjoy it?	3.5 ± 1.98	3.5 ± 1.87	4.0 ± 1.36	3.5 ± 1.46	3.2 ± 1.81	4.9 ± 1.44
Did it relieve the urge to smoke?	3.5 ± 1.98	3.6 ± 2.10	4.1 ± 1.79	3.3 ± 1.91	3.1 ± 2.11	5.5 ± 1.60
Was it enough nicotine?	3.1 ± 1.93	4.0 ± 1.96	4.3 ± 1.79	3.3 ± 1.99	3.2 ± 2.08	5.4 ± 1.55
Was it too much nicotine?	1.5 ± 0.97	2.5 ± 2.21	2.2 ± 1.66	1.7 ± 1.11	1.4 ± 0.63	2.4 ± 1.55

Summary of Subjective Effects Score by Study Product (Safety Population)

Scoring: 1 - Not at all, 2 - Very little, 3 - A little, 4 - Moderately, 5 - A lot, 6 - Quite a lot, 7 - Extremely. Scores are presented as mean \pm SD.

n = Number of subjects used in the analysis

Product A: *my*blu[™] closed system with CF Cosmic Fog Chilled Tobacco flavor, nicotine salt liquid 25 mg Product B: *my*blu[™] closed system with CF Cosmic Fog Chilled Tobacco flavor, non-nicotine salt liquid 25 mg Product C: *my*blu[™] closed system with CF Cosmic Fog Chilled Tobacco flavor, nicotine salt liquid 40 mg Product D: *my*blu[™] closed system with CF Cosmic Fog Chilled Tobacco flavor, nicotine salt liquid 16 mg Product E: blu PRO open system with Purilum Cosmic Fog Chilled Tobacco flavor, nicotine salt liquid 48 mg Product F: Subject's usual brand combustible cigarette

Overall, the study products were well-tolerated under the conditions of use in the study. There were no serious adverse events (SAEs) reported in the study, and no subjects were discontinued due to AEs. Product use emergent AEs were infrequently reported with four subjects reporting a total of 10 AEs. Vessel puncture site pain was the most frequently reported AE, experienced by two subjects. All remaining AEs were experienced by one subject each. All AEs were mild in severity, with the exception of moderate insomnia (blu PRO 48 mg). The PI considered one AE of headache (mybluTM 25 mg [non-salt formulation]) to be possibly related to study product and the remaining nine events unlikely or unrelated.

1.3 Rationale for the Study

This study is being conducted to provide information on the *my*blu[™] e-cigarette system with Tobacco Chill and Honeymoon flavor Intense e-liquids, and two nicotine strengths (2.5% and 4.0%). Along with other pre-clinical in vitro studies, clinical, and behavioral and population studies, the results of this study are intended to contribute to a body of evidence demonstrating the reduced exposure potential of these products. The data may be included in future premarket tobacco application submissions to the United States (US) Food and Drug Administration (FDA) Center for Tobacco Products. The endpoints to be assessed are based on the FDA Electronic Nicotine Delivery Systems Draft Guidance for Industry (May 2016).

2. STUDY OBJECTIVES AND ENDPOINTS

2.1 Study Objectives

The primary objective of this study is:

1. To assess the change-from-baseline differences in the primary tobacco-related BoE following a 28-day use period of *my*blu[™] e-cigarettes relative to smoking usual brand combustible cigarettes.

The secondary objectives of this study are:

- 1. To assess the change-from-baseline differences in the primary tobacco-related BoE following a 56-day use period of *my*blu[™] e-cigarettes relative to smoking usual brand combustible cigarettes.
- 2. To assess the change-from-baseline differences in the secondary tobacco-related BoE following 28-day and 56-day use periods of *my*blu[™] e-cigarettes relative to smoking usual brand combustible cigarettes.
- 3. To characterize the change in the primary and secondary BoE and BoPH during a 56-day period of use of *my*blu[™] e-cigarettes.
- 4. To assess the change-from-baseline differences in the primary and secondary tobaccorelated BoE between Day 28 and Day 56 in subjects using *my*blu[™] e-cigarettes.
- 5. To assess change-from-baseline differences in the BoPH following 28-day and 56-day use periods of *my*blu[™] e-cigarettes relative to smoking usual brand combustible cigarettes.
- 6. To assess change-from-baseline differences in physiologic endpoints following 28-day and 56-day use periods of *my*blu[™] e-cigarettes relative to smoking usual brand combustible cigarettes.
- 7. To assess elements of abuse liability, subjective effects, and perceptions associated with use of *my*bluTM e-cigarettes.
- 8. To characterize use of four *my*blu[™] e-liquids (Tobacco Chill and Honeymoon flavor Intense e-liquids, 2.5% and 4.0% nicotine) during a 56-day use period.
- 9. To characterize nicotine uptake from the *my*blu[™] e-cigarettes relative to an e-cigarette comparator (JUUL[®] Virginia Tobacco 5% nicotine) and usual brand combustible cigarettes.
- 10. To confirm the safety of *my*blu[™] e-cigarettes during a 56-day use period.

2.2 Study Hypothesis

The study hypothesis is that switching from usual brand combustible cigarettes to a mybluTM e-cigarette will result in a significantly larger decrease from baseline in the primary tobacco-related biomarkers following 28 days of use relative to the change associated with continuing to smoke combustible cigarettes. The following hypothesis will be tested independently for each mybluTM e-liquid.
H₀: $\Delta \mu_{\text{test}} = \Delta \mu_{\text{cont}}$

 $H_A: \Delta \mu_{test} > \Delta \mu_{cont}$

Where H₀ is the null hypothesis, H_A is the alternative hypothesis, $\Delta \mu$ = the mean decrease from baseline, "test" = *my*bluTM product, and "cont" = combustible cigarette

2.3 Study Endpoints

2.3.1 Primary Study Endpoints

Biomarkers of Exposure

Biomarker	Matrix	Chemical Constituent
СОНЬ	Blood	СО
NNAL	Urine	NNK
3-НРМА	Urine	Acrolein
S-PMA	Urine	Benzene

2.3.2 Secondary Study Endpoints

Biomarkers of Exposure

Biomarker	Matrix	Chemical Constituent
NNN	Urine	NNN
CEMA	Urine	Acrylonitrile
HEMA	Urine	Ethylene oxide
НМРМА	Urine	Crotonaldehyde
MHBMA	Urine	1,3 butadiene
1-OHP	Urine	Pyrene
o-tol	Urine	Toluidine
3-OH B[a]P	Urine	B[a]P
1-AN	Urine	Naphthalene
2-AN	Urine	Naphthalene
Nicotine equivalents	Urine	Nicotine

Biomarkers of Potential Harm

Biomarker	Matrix	Biological Effect
sICAM	Blood	Inflammation
WBCs	Blood	Inflammation
HDL-C	Blood	Inflammation
MCP-1	Blood	Inflammation
8-epi-prostaglandin $F_{2\alpha}$	Urine	Oxidative stress
11-dehydrothromboxane B ₂	Urine	Platelet activation

Physiological Assessments

- FeNO
- Blood pressure
- Heart rate

Subjective Measures

- PSCDI/PSECDI
- Cough Questionnaire
- QSU-Brief
- MTWS-R
- PES
- Product Liking Questionnaire
- Future Intent to Use Questionnaire
- Product and Health Effect Perceptions Questionnaire

Product Use

Daily in-clinic product use documented by the clinic staff:

- Number of cigarettes smoked
- Number of *my*bluTM pods started
- *my*blu[™] pod weight change (for pods used during the 24 hour urine collections)
- Day 3 and Day 29 product preference selection

Daily product use endpoints documented by subjects (Day 3 through study discharge on Day 57):

- Number of cigarettes smoked
- Number of *my*bluTM pods started
- Number of puffs from the *my*bluTM product daily (< or \ge 50 puffs)

Nicotine PK Assessments

Product use during each product use session:

- Number of puffs taken
- my bluTM and JUUL[®] pod weight change

Page 37 CA22747_PROTOCOL AMENDMENT 3_24MAR2020 PK parameters during each product use session:

- C_{max}
- AUC_{0-t}
- T_{max}

Urge to smoke parameters during each product use session:

- Maximum reduction from baseline score (E_{max_R})
- Time of the E_{max_R} (TE_{max})
- Area under the change from baseline "Urge to Smoke" VAS score versus time curve (AUEC_BL)

Other Compliance Assessments

- Exhaled CO
- Urine cotinine

Safety

Safety assessments will include physical examinations, vital signs, ECGs, clinical laboratory tests, lung function, pregnancy tests, AEs, and use of concomitant medications.

3. SUMMARY OF STUDY DESIGN

3.1 Design and Procedures

This will be an open-label, partially-randomized, parallel-arm, multi-site study in healthy adult smokers, consisting of the main study and a PK sub-study.

The main study will assess BoE, BoPH, physiologic effects, and subjective effects with use of *my*bluTM e-cigarettes relative to continuing to smoke combustible cigarettes. To account for potential attrition, up to 175 subjects are planned to be randomized into the *my*bluTM arm (with approximately 43 subjects intended to be assigned to each *my*bluTM e-liquid) and up to 40 subjects will be randomized into the continue-smoking arm. Baseline study assessments will be made during use of subjects' usual brand combustible cigarettes during the initial test visit through the morning of Day 1. All subjects in the *my*bluTM and continue-smoking arms will return to the clinic site for test visits scheduled to occur on Days 14, 28, 42, and 56 for post-baseline study assessments, compliance checks, and product dispensing and return. The subset of subjects participating in the PK sub-study (described below) will also complete selected biomarker assessments (NNAL, NNN, 3-HPMA, CEMA, HMPMA, S-PMA, nicotine equivalents) on Days 3 and 4.

Subjects randomized to the *my*bluTM arm will participate in an in-clinic product acclimation period from Days 1 to 3. The acclimation period will afford the subjects the opportunity to try each of the four *my*bluTM e-liquids in order to become accustomed to their use and to determine those that they would be willing to use during the study. Initial product assignment for each subject will be based on preference as a method to enhance compliance. To further improve compliance through Day 56, at the end of Test Visit 3, subjects using a *my*bluTM

product may be allowed to choose to switch to the alternate nicotine strength of their current flavor, to switch to the alternate flavor with the same nicotine strength as their initial choice, or to continue using the same e-liquid selected initially. This method for initial flavor assignment and the opportunity to re-select after 28 days of use is based on natural experimentation that consumers experience when choosing an e-cigarette flavor.

The PK sub-study will assess nicotine uptake and urge to smoke from the *my*blu[™] products relative to combustible cigarettes and an e-cigarette comparator (JUUL[®]). A subset of up to 20 subjects assigned to each of the my bluTM e-liquids, 20 subjects from the continue-smoking arm, and all 20 subjects in the JUUL[®] arm will participate. Subjects in the JUUL[®] arm will begin using the product after check-in for Test Visit 1 and will continue to use the product through discharge on Day 1 from the study following the PK assessment (subjects in the JUUL® arm will only participate in the PK sub-study). PK assessments will be preceded by a minimum 10-hour abstention from product use and will take place on Day 1 for the JUUL® and continue-smoking arms, and on Day 5 for the *my*blu[™] arm. Product use for the PK assessments will consist of two sessions: 1) a fixed puffing session in the morning consisting of 10 puffs taken at 30 second intervals, with puffs 3 seconds in duration, and 2) an ad *libitum* use session beginning 6 hours after the start of the morning session and consisting of unlimited use of the e-cigarette product for 5 minutes or one cigarette, with no limits on puff duration or inter-puff interval. No product use of any kind will be allowed between the sessions. E-cigarette pods used for each session will be weighed before and after use to measure the amount of e-liquid used.

All product use during confinement will be documented by the clinic staff. Subjects in the mybluTM and continue-smoking arms will be required to self-report product use from Day 3 through discharge from the study.

Exhaled CO and urine cotinine measurements will be used to confirm smoking/nicotine use status prior to Day 1 and to assess subject compliance with product assignment requirements thereafter.

The clinic staff will contact all subjects via a telephone call approximately 14 days after discharge from the study (either as scheduled or after early termination) for reporting of AEs and use of concomitant medications.

Screening safety evaluations will include a physical examination, vital signs, ECG, clinical laboratory tests (clinical chemistry, hematology, urinalysis, and serology), lung function, urine drug tests, urine cotinine tests, and alcohol breath tests, FSH tests (post-menopausal females) and serum and urine pregnancy tests (females only). On-study safety evaluations will include a symptom-driven physical examinations, vital signs, ECG, clinical laboratory tests (clinical chemistry, hematology, and urinalysis), lung function, and urine pregnancy tests (females only). AEs spontaneously reported by the subjects or observed by the Investigator or other study personnel will be documented and monitored from the time of first product use after successful completion of the check-in events for Test Visit 1 through the end of the Follow-up Period. Any prior and concomitant medications taken from 30 days prior to Screening through the Follow-up Period will also be recorded.

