	Blood sampling	Per sampling schedule
	Urge to smoke assessment	Per sampling schedule
~18:00	Discharge continue-smoking and JUUL® subjects following completion of PK assessments Symptom-driven physical Vital signs Review of tobacco and nicotine restrictions Subject cigarettes returned	Discharge events may be completed prior to 18:00
Day 2		
	Document AEs and medications	Throughout the day
07:00 - 23:00	Product use	
After 20:00	my blu [™] test product preference selection	
Day 3		
	Document AEs and medications	Throughout the day
07:00 - 23:00	Product use	Day 3 subject self-reporting to be confirmed by clinic staff.
19:00 - 20:00	Start of 24-hour urine collection	Only my blu™ subjects continuing into the PK assessment
19:00 - 20:00	Questionnaires administered (QSU-Brief, MTWS-R, PES, Product Liking)	All myblu™ subjects
~20:00	Discharge my blu [™] subjects not participating in PK assessments Exhaled CO Symptom-driven physical Vital signs Review of tobacco and nicotine restrictions Test product dispensing	Discharge events may be completed prior to 20:00. Subjects must be seated for at least 5 minutes prior to vital signs measurement, and must be collected at least 15 minutes after the last study product used.
Day 4		
	Document AEs and medications	Throughout the day

Time	Procedures	Comments
07:00 - 23:00	Product use	
17:00 - 18:00	Blood sample collection for COHb	
19:00 - 20:00	End of 24-hour urine collection	± 30 minutes from the start time on Day 3
Day 5		
	Document AEs and medications	Throughout the day
09:00	Fixed puffing PK session	Follows a 10-hour abstention from product use.
	Product use documentation	
	Blood sampling	Per sampling schedule
15:00	Ad libitum puffing PK session	To begin ~6 hours following the start of the fixed puffing regimen.
	Product use documentation	
	Blood sampling	Per sampling schedule
	Urge to smoke assessment	Per sampling schedule
~18:00	Discharge subjects Exhaled CO Symptom-driven physical Vital signs Review of tobacco and nicotine restrictions Test product dispensing	Discharge events may be completed prior to 18:00. Subjects must be seated for at least 5 minutes prior to vital signs measurement, and must be collected at least 15 minutes after the last study product used.

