To further improve compliance through Day 56, during the Day 28 visit subjects using a mybluTM product may be allowed to choose to switch to the alternate nicotine strength of their current flavor, to switch to the alternate flavor with the same nicotine strength as their initial choice, or to continue using the same e-liquid selected initially. Subjects will be allowed a brief trial with the alternate products if desired. The site staff will document this use, but subjects will not need to report these as a part of their product use reporting.

Usual Brand Cigarette Use

Subjects randomized to the continue-smoking arm will smoke their usual brand cigarettes throughout each confinement visit. Subjects will turn-over all cigarettes upon check-in to each test visit.

JUUL[®] Product Use

Subjects in the JUUL[®] arm will begin using the product following the demonstration and training on Day -2 and will continue to use the product through 23:00 on Day -1. Subjects in the JUUL[®] arm will not be allowed to smoke at any time from the time of check-in on Day -2 through discharge on Day 1.

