Appendix 11: Urge to Smoke Questionnaire

Note: The following question will be paired with a VAS. The VAS will be anchored with "Not at All" on the left and "Extreme" on the right.

Please respond to the question by drawing a vertical mark anywhere along the horizontal line.

How strong is your urge to smoke right now?

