# 6.6 Urge to Smoke

#### **6.6.1** Urge to Smoke Parameters

Urge to smoke will be assessed using a 100 mm VAS approximately 10 minutes prior to and within approximately 30 seconds prior to the scheduled blood draws at 5, 10, 15, 30, 60, and 120 minutes following the start of the *ad libitum* product use session.

The following parameters will be calculated for the urge to smoke assessments performed during the PK assessments.

 $E_{max\_R}$  The maximum reduction from baseline VAS score (VASpre-use – VASpost-use).

TEmax Time of the  $E_{max\_R}$ . If the maximum value occurred at more than one time point,  $TE_{max}$  will be defined as the first time point with this value.

AUEC\_0-120\_R The area under the reduction from baseline "Urge to Smoke" VAS score (VASpre-use – VASpost-use) versus time curve from 0 to 120 minutes, calculated using the linear trapezoidal method with linear interpolation using actual sample times

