# Statistical Analyses of Pharmacokinetics (*my*bluTM Products Versus the Continuesmoking arm or JUUL arm)

A linear mixed model ANOVA will be performed on the log-transformed nicotine PK parameters AUC and Cmax from each product use session (PK population). The model will include product arm as a fixed effect. Geometric LSMs will be provided for the PK parameters of Cmax and AUC by product arm. Geometric LSM ratio, 95% confidence intervals of geometric LSM ratio, and p-values will be provided for the product arm comparisons for Cmax and AUC. The comparisons of interest will include each of the *my*bluTM product arms compared to continue-smoking arm or JUUL arm. The above statistical analyses will be performed using the following SAS codes.

```
Proc MIXED data=<>;
Class subject arm;
Model LN_dependent variable = arm/DDFM=KR;
LSMeans arm/pdiff CL alpha=0.05;
Run;
```

Non-parametric analysis (Wilcoxon Rank Sum test) will be performed for the comparisons of  $T_{max}$  between test and reference products.

Similar methods will be used to compare the urge to smoke parameters.

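### Urge-to-smoke reductions are compared without the pre-use VAS score that bounds them, although the schedule does not make that score comparable across arms

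*Protocol*

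**What the plan says.** **Timing.** Under Protocol 3.1 the PK assessments "will take place on Day 1 for the JUUL® and continue-smoking arms, and on Day 5 for the" myblu arm, with the ad libitum "use session beginning 6 hours after the start of the morning session". The Test Visit 1 schedule (Protocol 6.1.2, Table 5) puts the fixed session at 09:00 and the ad libitum session at 15:00; its Day 5 entry reads "To begin ~6 hours following the start of the fixed puffing regimen". In the interval, "No product use of any kind will be allowed between the sessions".

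**Access to cigarettes.** Continue-smoking subjects smoke in the 09:00 session itself. JUUL subjects "will not be allowed to smoke at any time from the time of check-in on Day -2 through discharge on Day 1" (Protocol 6.3.1). Under the same section, myblu subjects may smoke until 23:00 on Day -1 and then change to the test products.

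**Outcome.** The item is "How strong is your urge to smoke right now" (Protocol Appendix 11), on a 100 mm VAS. It is scored about 10 minutes before the ad libitum session and at set times up to 120 minutes. SAP 6.6.1 defines E_max_R as "The maximum reduction from baseline VAS score (VASpre-use – VASpost-use") and AUEC_0-120_R as the area under that same difference.

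**Analysis.** SAP 6.7.2 gives a PK model with product arm as its fixed effect and then adds: "Similar methods will be used to compare the urge to smoke parameters". The contrasts are each myblu product against continue-smoking and against JUUL. The shell that Table 14.2.5.13 shares with the PK comparison tables carries a footnote describing another model: arm, study day, their interaction, a random subject effect and log-transformed parameters.

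**The concern.** The common abstention period aligns the arms on time since nicotine. The question, however, is about the urge to smoke, and the arms differ widely in time since a cigarette. The design therefore gives no assurance that pre-use scores are alike. Assignment does not give it either: the e-liquid is chosen by preference, and the first eligible subject in each sex-age stratum at a site may be placed in the JUUL arm (Protocol 4.5).

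The outcome is a raw drop from the pre-use score, so an arm that starts lower has less room to fall. If starting levels differ, a myblu-versus-cigarette or myblu-versus-JUUL contrast may appear, or be hidden, for a reason other than the product's capacity to relieve the urge.

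**Working it through.** **1. Intervals at the ad libitum session.** Protocol 6.7.3 and SAP 6.6.1 collect urge scores only around this session. There is no Day 0.

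- Continue-smoking: 09:00 to 15:00 on Day 1 = 6 h, which reproduces the protocol's stated 6 hours.
- JUUL: last cigarette at or before check-in on Day -2. No clock time is given; Protocol Table 3 asks only that check-in be as early as possible. Assumed 14:00: 48 h to 14:00 on Day 1, plus 1 h = 49 h. Assumed 07:00: 48 + 8 = 56 h.
- myblu: 23:00 on Day -1 to 23:00 on Day 4 = 96 h, plus 16 h to 15:00 on Day 5 = 112 h, as a minimum.
- Time since any product: about 6 h in every arm, because each uses its own product at 09:00 and nothing afterwards.

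**2. Bounds.** A VAS score cannot be below 0, so pre-use minus post-use cannot exceed pre-use. Hence E_max_R ≤ pre-use score, and AUEC_0-120_R ≤ about 120 min × pre-use score. TE_max is a time and has no such bound.

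**3. Do the stated models deal with this?** The model in SAP 6.7.2 has arm only. In the shell footnote, study day adds nothing: each arm has a single PK day, so day is aliased with arm, and each subject has one record per parameter. Neither version contains the pre-use score.

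**4. Size under stated assumptions.** If two products remove the same share r of the urge and mean pre-use scores differ by d, the raw contrast is r × d for E_max_R and at most about 120 × r × d for AUEC_0-120_R. The values of r and d below are assumptions; the documents give none.

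| d (mm) | E_max_R contrast at r = 30% / 50% / 70% (mm) | AUEC contrast, upper limit (mm·min) |
|---|---|---|
| 10 | 3 / 5 / 7 | 360 / 600 / 840 |
| 20 | 6 / 10 / 14 | 720 / 1200 / 1680 |

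With 20 per group (Protocol 3.1, up to 20 per e-liquid) and an assumed SD of 25 mm for the reduction, the SE of a contrast is 25 × √(2/20) = 7.9 mm. A 5 mm shift is then about 0.6 SE (5/7.9).

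**5. Simulation.** Two arms of 20; equal 50% mean relief with SD 0.25; pre-use SD 25 mm; 4000 runs. All but the arm size are assumptions.

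| Pre-use gap (mm) | Arm-only contrast (mm) | p<0.05, arm only | p<0.05, with pre-use covariate |
|---|---|---|---|
| 0 | -0.1 | 5% | 5% |
| 10 | 4.8 | 12% | 5% |
| 20 | 9.2 | 32% | 5% |
| 30 | 13.9 | 61% | 4% |

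With the covariate the mean contrast stayed within 0.2 mm of zero at every gap.

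**The case against.** The strongest reply is that the plan already equalises the main acute driver. All arms abstain for at least 10 hours before the fixed session and use nothing between sessions, so nicotine deprivation is matched. JUUL and myblu subjects have nicotine available during their cigarette-free hours, and habituation could lower their urge as easily as deprivation could raise it. This stands. A reader might infer from the 6, 49 to 56 and 112 hours that the contrast is biased, or biased in a known direction. The documents do not support that, because they give no pre-use score for any arm.

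A second reply is that the covariate is no clean remedy. In every arm the pre-use score follows use of the assigned product; for myblu it follows several days of it. Conditioning on it may remove part of a product effect, and the groups are not fully randomised. This also stands, and it limits the claim: adjustment cannot separate testing day from product. It is not a reason to leave the score out, since the planned outcome already subtracts that same score. The simulated return to about zero also depends on the assumption of equal proportional relief.

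Third, imbalance would be visible. Tables 14.2.5.1 to 14.2.5.6 use a shell with a pre-use column, and Figure 14.2.11.1 plots unadjusted urge by product. That is correct, but these displays are descriptive and do not alter Table 14.2.5.13.

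Finally, these are secondary endpoints without a power statement, and the Day 28 biomarker analysis is untouched. That bears on priority, not on whether the gap exists.

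**Conclusion.** The point holds in limited form. The schedule does not make the pre-use score comparable across arms, E_max_R and AUEC_0-120_R are bounded by it, and no stated model includes it. Unequal pre-use means would carry straight into the raw contrasts: 3 to 7 mm of E_max_R per 10 mm of gap, for assumed relief of 30% to 70%. Whether such a gap exists, and in which direction, cannot be known from the documents; with equal means the effect is zero.

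It would also go too far to say that arm is certainly the only model term. SAP 6.7.2 promises similar methods, not the identical model, and the shell footnote lists others. None of the listed terms adjusts for starting urge, so the conclusion is the same under either version. The two texts conflict and need reconciling in any case.

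**What to change.** - In SAP 6.7.2, prespecify for E_max_R and AUEC_0-120_R a model with product arm plus the pre-use VAS score as covariate. Report its LS mean differences beside the unadjusted ones in Table 14.2.5.13. TE_max needs no such term.
- Reconcile the shell footnote with SAP 6.7.2 for these parameters: study day, the interaction, the random subject effect and the log transform. A log is undefined for a zero reduction, which Protocol 7.4.6 allows by its floor on E_max_R, and for a negative value, which SAP 6.6.1 does not exclude.
- Add a footnote to Table 14.2.5.13 giving hours since last cigarette per arm. It should say that the pre-use score is measured after use of the assigned product, so adjustment does not separate testing day from product.
- Cross-refer to Tables 14.2.5.1 to 14.2.5.6 for pre-use scores by product; no new table is needed.

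The cost is SAP wording and one covariate (1 df) from data already collected, with no change to procedures. If pre-use score and reduction correlate at an assumed 0.6, the SE would also fall from 7.9 to about 6.3 mm (7.9 × √(1 - 0.36)).
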